12.4.3 Serious Adverse Event Reporting

An SAE occurring from the first dose administered until Day 28 must be reported to EVERSANA Pharmacovigilance and will be communicated to the Sponsor. Any such SAE due to any cause, whether or not related to the study drug, must be reported within 24 hours of occurrence or when the investigator becomes aware of the event. Notification can be made using the dedicated fax line or email for the EVERSANA Pharmacovigilance group:

EVERSANA Pharmacovigilance [contact]

EVERSANA Pharmacovigilance email address: [contact]

If the investigator contacts the EVERSANA Pharmacovigilance group by telephone, then a written report must follow within 24 hours and is to include a full description of the event and sequelae in the format detailed in the SAE reporting form.

EVERSANA Pharmacovigilance [contact]

The event must also be recorded on the standard AE eCRF. Preliminary reports of SAEs must be followed up by detailed descriptions later on, including clear and anonymized photocopies of hospital case reports, consultant reports, autopsy reports, and other documents when requested and applicable. SAE reports must be made whether or not the investigator considers the event to be related to the investigational drug.

Appropriate remedial measures should be taken to treat the SAE, and the response should be recorded. Clinical, laboratory, and diagnostic measures should be employed as needed in order to determine the etiology of the problem. The investigator must report all additional follow-up evaluations to the EVERSANA Pharmacovigilance group within 24 hours of becoming aware of the additional information or as soon as is practicable. All SAEs will be followed up until the investigator and Sponsor agree the event is satisfactorily resolved.

Any SAE that is not resolved by the end of the study or upon discontinuation of the subject's participation in the study is to be followed up until it either resolves, stabilizes, returns to baseline values (if a baseline value is available), or is shown to not be attributable to the study drug or procedures.

12.4.4 Suspected Unexpected Serious Adverse Reactions

Adverse events that meet all of the following criteria will be classified as suspected unexpected serious adverse reactions (SUSARs) and reported to the appropriate regulatory authorities in accordance with applicable regulatory requirements for expedited reporting:

- serious
- unexpected (i.e., the event is not consistent with the safety information in the IB)
- there is at least a reasonable possibility that there is a causal relationship between the event and the study treatment

The investigator will assess whether an event is causally related to study treatment. The Sponsor (or EVERSANA) will consider the investigator's assessment and determine whether the event meets the criteria for being reportable as a 7-day or 15-day safety report. SUSARs that are life-threatening must be reported to the regulatory authorities and the institutional review board (IRBs; where required) within 7 days after the Sponsor (or EVERSANA) has first knowledge of them, with a follow-up report submitted within a further 8 calendar days. Other SUSARs must be reported to the relevant regulatory authorities and the IRBs within 15 calendar days after the Sponsor (or EVERSANA) first has knowledge of them.

The Sponsor (or EVERSANA) is responsible for reporting SUSARs and any other events required to be reported in an expedited manner to the regulatory authorities and for informing investigators of reportable events, in compliance with applicable regulatory requirements within specific timeframes. Investigators will notify the relevant IRBs of reportable events within the applicable timeframes.

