12.4.2 Serious Adverse Events

In general for any clinical trial an SAE is any untoward medical occurrence, in the view of either the investigator or Sponsor, that:

- results in death,
- is life-threatening,
- results in inpatient hospitalization or prolongation of existing hospitalization,
- results in persistent or significant disability/incapacity, and/or
- is a congenital anomaly/birth defect

For the purposes of this study, death and inpatient hospitalization will not be considered as an SAE, as the primary end point of this study is the proportion of subjects requiring COVID-19 related hospitalization (including emergency room visit) or who die due to any cause within 28 days of randomization

Other important non-COVID-19 medical events that may not be immediately life-threatening or result in death or hospitalization, based upon appropriate medical judgment, are considered SAEs if they are thought to jeopardize the subject and/or require medical or surgical intervention to prevent one of the outcomes defining an SAE. SAEs are critically important for the identification of significant safety problems; therefore, it is important to take into account both the investigator's and the Sponsor's assessment. If either the Sponsor or the investigator believes that an event is serious, the event must be considered serious and evaluated by the Sponsor for expedited reporting.

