4.3 ANALYSES OF SAFETY/TOLERABILITY

As stated in the Clinical Protocol NI03-CV19-001 Version 4.0, all reported AEs will be coded using the latest version of the Medical Dictionary for Regulatory Activities (MedDRA). The incidence of Treatment Emergent Adverse Events (TEAEs) will be included in incidence tables. Events with missing onset dates will be included as treatment emergent. If a subject experiences more than 1 occurrence of the same AE, the occurrence

⁵ Kaplan EL and Meier P. Nonparametric estimation from incomplete observations, Journal of the American Statistical Association, 53:457-481, 1959.

⁶ Cox DR. Regression models with life-tables (with discussion), Journal of the Royal Statistical Society, B. 66:188-90, 1972.

with the greatest severity and the closest association with the study drug will be used in the summary tables. SAEs, Common Terminology Criteria for Adverse Events (CTCAE) grades 3, 4, or 5 TEAEs, and TEAEs causing discontinuation will be summarized using discrete summaries by system organ class and preferred term for each treatment group. All AEs will be listed by subject, along with information regarding onset (study day), duration, relationship and severity to study drug, action taken with study drug, treatment of event, and outcome.

Treatment emergent adverse events (TEAEs) are defined as all adverse events that occur after first study treatment (either active or placebo). TEAEs will be summarized by severity and relationship separately.

All adverse events that lead to death or are life threatening will be recorded as Serious Adverse Events in the SDTM datasets. Only non-COVID related Serious Adverse Event (SAE's) will be included in the summaries provided below.

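### Protocol 12.4.2 takes death and hospitalization out of the SAE definition without limit and 12.4.4 names no clock for a fatal suspected reaction, while SAP 4.3 records fatal events as SAEs

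*Protocol*

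**What the plan says.** Protocol 12.4.2 opens with a general list of SAE criteria in which a fatal outcome and a life-threatening event are separate items. It then sets a rule for this study: "death and inpatient hospitalization will not be considered as an SAE". The reason given is that the primary endpoint consists of COVID-19 related hospitalization (emergency room visits included) or death from any cause. The same section adds an override: "If either the Sponsor or the investigator believes that an event is serious, the event must be considered serious", and the Sponsor must then evaluate the event for expedited reporting.

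Protocol 12.4.3 requires SAEs to reach the pharmacovigilance vendor within 24 hours, whether or not they are related to study drug.

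Protocol 12.4.4 makes an adverse event a SUSAR only if it is serious, unexpected and possibly caused by study treatment. SUSARs are to be "reported to the appropriate regulatory authorities in accordance with applicable regulatory requirements for expedited reporting". Two clocks follow, both counted from first knowledge by the Sponsor or vendor: "SUSARs that are life-threatening must be reported to the regulatory authorities" (and to IRBs where required) within 7 days, with a follow-up report within 8 further calendar days, and "Other SUSARs must be reported to the relevant regulatory authorities and the IRBs within 15 calendar days".

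SAP 4.3 says: "All adverse events that lead to death or are life threatening will be recorded as Serious Adverse Events", and places that recording in the SDTM datasets. It then restricts the SAE summaries to non-COVID events.

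**The concern.** Keeping endpoint events out of routine SAE handling is understandable when they are expected consequences of the disease. Here the exemption is broader than that purpose needs. The endpoint counts death from any cause, so the exemption also covers a death that the investigator attributes to study drug. For hospitalization it goes beyond its own justification: the endpoint counts only COVID-19 related admissions, yet the exemption says inpatient hospitalization without qualification.

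Both the 24-hour site notice and SUSAR status depend on an event being serious, so a gap in the SAE definition carries into expedited reporting. The protocol's own risk section (5.3) lists serious post-marketing reactions: shock and anaphylaxis, thrombocytopenia, hepatic disorder and hyperkalemia. A suspected fatal reaction is therefore not a remote hypothetical. At stake are the safety of subjects still on treatment and consistent handling across up to about 25 sites.

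**Working it through.** No sample-size, power or alpha figure is involved. The check sets the sections side by side and follows one case through them: a death during the study, unexpected against the Investigator's Brochure, with a reasonable possibility of causation by study drug.

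**Step 1. Is it an SAE?** The general list in 12.4.2 has five criteria: death, life-threatening, inpatient or prolonged hospitalization, disability, congenital anomaly. The study-specific rule removes death and inpatient hospitalization. Death alone is then no ground for SAE status. The event can still qualify as life-threatening, through the medical-judgment clause, or through the override.

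**Step 2. Does the site owe a 24-hour notice?** Section 12.4.3 applies to SAEs. If the site follows the rule in Step 1 and uses no other ground, the notice is not triggered. The clocks in 12.4.4 start only when the Sponsor or vendor knows of the event, so the start of the clock is affected too. SAP 3.1 has deaths recorded on the End of Study form, but that is not a 24-hour route.

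**Step 3. Is it a SUSAR?** Seriousness is one of three criteria that must all be met. On the ground of death alone it fails after Step 1.

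**Step 4. If it is accepted as serious, which clock?** Section 12.4.4 splits SUSARs into life-threatening and other. Fatal SUSARs are not named. Section 12.4.2 treats a fatal outcome and a life-threatening event as different criteria, so the protocol's own usage does not clearly put one inside the other.

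| Reading of the fatal reaction | Serious? | 24-hour notice? | First expedited report |
|---|---|---|---|
| 12.4.2 applied literally, death the only ground | No | Not triggered | No SUSAR clock |
| Judged serious under the override, treated as other | Yes | Yes | 15 days |
| Regarded as life-threatening before death | Yes | Yes | 7 days |

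Difference between the two stated clocks: 15 - 7 = 8 days. This concerns the first report only. The follow-up to a 7-day report falls due at 7 + 8 = 15 days, so both routes reach the same day for the fuller report.

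**Step 5. Does the SAP agree?** SAP 4.3 records every adverse event leading to death as an SAE, with no condition on relatedness, and pairs fatal with life-threatening events. Protocol 12.4.2 says death is not an SAE. Other text also presupposes fatal SAEs or drug-related deaths: 12.4.3 asks for autopsy reports in SAE follow-up, and SAP 4.3.1 has a row for drug-related death.

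**The case against.** The strongest reply is that the protocol contains enough to handle the case correctly. A reaction that kills was ordinarily life-threatening first, and that criterion survives the exemption. On this reading the event is serious, can be a SUSAR and takes the 7-day clock. The override lets either party make the event serious. Section 12.4.4 defers to applicable regulatory requirements and makes the Sponsor responsible for any other event that requires expedited reporting. Section 14.1.1 binds the trial to the federal regulations it lists. On SAE coding, protocol section 13 and SAP section 1 both give the SAP precedence.

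Much of this stands. A reader might infer that fatal reactions are assigned to the slower clock, or would not be reported at all. The documents do not support either as an established effect. Each is one literal reading among several, and deaths also appear in the primary endpoint, the adverse event summary and the Listing of Deaths.

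A reader might also infer that the absence of an interim analysis makes this worse. It does not bear on the point: expedited reporting works case by case, and an interim look would not replace it.

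What the reply does not remove is the contradiction. The override is a matter of judgment and follows an explicit statement that death is not an SAE. The regulatory reference is general, while the clocks beside it are specific and omit the fatal case. SAP precedence settles dataset coding, but SAP 4.3 does not address when a site must call.

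**Conclusion.** The rule is wrong as written. Followed literally, 12.4.2 takes a death suspected to be drug-caused out of the 24-hour notice and out of SUSAR status unless someone invokes another ground of seriousness. Section 12.4.4 leaves the clock for a fatal SUSAR unstated, and SAP 4.3 contradicts 12.4.2 on whether a fatal event is an SAE.

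The effect lies between none (the event is treated as life-threatening) and no SUSAR clock (the exemption applied literally), with an 8-day later first report in between. The documents do not say which reading sites would use, so no single figure can be claimed. The conclusion rests on the wording of these sections alone and assumes no outside regulation. Sample size, power and the primary analysis are unaffected.

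**What to change.** Reconcile protocol 12.4.2, 12.4.3 and 12.4.4 with SAP 4.3:

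- **SAE status.** Give a fatal adverse event one explicit status that agrees with SAP 4.3. Do not make that status depend on relatedness. SAP 4.3 has no such condition and 12.4.3 requires reports regardless of relation, so a causality filter would leave one conflict in place and add another.
- **Endpoint exemption.** If 12.4.2 keeps an exemption for endpoint events, bound it explicitly, for hospitalization as well as death, so that it cannot remove a suspected drug reaction from SAE or expedited reporting.
- **Clock.** State in 12.4.4 which clock applies to a fatal SUSAR, in line with the regulatory requirements that the section already cites.

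The cost is a wording amendment and a note to sites. No change to the endpoint, the sample size or the analysis is needed.

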12.4.5 Pregnancy

WOCBP must have a negative urine pregnancy test at screening. Following administration of study drug, any known cases of pregnancy in female subjects will be reported until the subject completes or withdraws from the study. The pregnancy will be reported immediately by faxing/emailing a completed pregnancy report to the Sponsor (or EVERSANA) within 24 hours of knowledge of the event. The pregnancy will not be processed as an SAE; however, the investigator will follow up with the subject until completion of the pregnancy and must assess the outcome in the shortest possible time but not more than 30 days after completion of the pregnancy. The investigator should notify the Sponsor (or EVERSANA) of the pregnancy outcome by submitting a follow-up pregnancy report. If the outcome of the pregnancy involved spontaneous or therapeutic abortion (any congenital anomaly detected in an aborted fetus is to be documented), stillbirth, neonatal death, or congenital anomaly, the investigator will report the event by faxing/emailing a completed pregnancy report form to the Sponsor (or EVERSANA) within 24 hours of knowledge of the event.

If the investigator becomes aware of a pregnancy occurring in the partner of a subject participating in the study, the pregnancy should be reported to the Sponsor (or EVERSANA)

within 24 hours of knowledge of the event. Information regarding the pregnancy must only be submitted after obtaining written consent from the pregnant partner. The investigator will arrange counseling for the pregnant partner by a specialist to discuss the risks of continuing with the pregnancy and the possible effects on the fetus.

Upon discontinuation from the study, only those procedures that would not expose the subject to undue risk will be performed. The investigator should also be notified of pregnancy occurring during the study but confirmed after completion of the study. In the event that a subject is subsequently found to be pregnant after inclusion in the study, any pregnancy will be followed to term, and the status of mother and child will be reported to the Sponsor after delivery.

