7.3 End of Study

A subject will have fulfilled the requirements for study completion if/when the subject has completed all study periods, including the end of study visit on Day 28, which is the last

scheduled visit as indicated in the Schedule of Assessments (Table 1). Subjects who terminate prior to completing the 14-day treatment period are asked to complete the Early Termination visit.

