- ^a Denotes a baseline assessment. Baseline is defined as before the first dose of study drug. Baseline assessments should be performed before administration of study drug. Subjects are enrolled following completion of eligibility requirements and who are randomized in the IWR. Subjects who are screened to determine eligibility, but do not undergo any baseline assessments are not considered enrolled. All eligible subjects must have documented COVID-19 infection diagnosed at the local level.
- ^b Study Day 1= first dose of study drug.
- ^c Assessments to be done daily.
- ^d X = clinic visit, ☎ = telephone visit. All post-baseline visits are ± 1 day in the event a visit occurs on a weekend.
- ^e Subjects will be given access and instructions to complete their eDiary on Day 1 using the web portal. Subjects will complete their eDiary daily from Day 1 through Day 15, Data to be collected in the eDiary daily will include 1) the number of study medication doses taken/missed and 2) the highest temperature recorded over the past 24 hour period.
- ^f All AEs must be recorded from the time of administration of the first dose of study drug until the subject has completed the end of study or early withdrawal. Any study procedure-related SAE that occurs after the study participant has signed the informed consent form and prior to administration of the first dose of study drug will be considered as Medical History. The study will collect only Treatment Emergent Adverse Events (TEAE).
- ^g Laboratory assessments including hematology (CBC including hemoglobin, hematocrit, WBC with differential, RBC, MCV, and platelet count) and clinical chemistry (albumin, ALT, ALP, AST, BUN, GGT, creatinine, electrolytes [sodium, potassium, carbon dioxide, chloride], glucose, total bilirubin, direct bilirubin, LDH, CRP) will be collected. Laboratory tests will be performed at the central laboratory.
- ^h Absence of fever is defined as ≤ 37.2°C oral.
- ⁱ The indicated assessments may be done at the investigators discretion but are not required.

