16.1 APPENDIX 1 - CONTRACEPTION GUIDELINES

Women of childbearing potential (WOCBP) and men whose sexual partners are WOCBP must use at least 1 highly effective method of contraception during the study and for 90 days after the last dose of study treatment.

A woman is considered to be a WOCBP (fertile) following menarche and until becoming postmenopausal, unless she is permanently sterile. Permanent sterilization methods include hysterectomy, bilateral salpingectomy, and bilateral oophorectomy. A postmenopausal state is defined as no menses for 12 months without an alternative medical cause. A high follicle-stimulating hormone (FSH) level in the postmenopausal range may be used to confirm a postmenopausal state in women not using hormonal contraception or hormonal replacement therapy. However, in the absence of 12 months of amenorrhea, a single FSH measurement is insufficient.

A man is considered fertile after puberty unless permanently sterile by bilateral orchidectomy.

Highly effective methods of contraception are those which have a failure rate of <1% (when implemented consistently and correctly) and include:

- combined (containing estrogen and progestogen) hormonal contraception associated with inhibition of ovulation (administration may be oral, intravaginal, or transdermal)
- progestogen-only hormonal contraception associated with inhibition of ovulation (administration may be oral, injectable, or implantable)
- intrauterine device
- intrauterine hormone-releasing system
- bilateral tubal ligation or occlusion
- vasectomy (provided that the male has a medical assessment of surgical success)
- sexual abstinence (defined as refraining from heterosexual intercourse during the entire period of risk in relation to the duration of the clinical trial, in line with the preferred and usual lifestyle of the subject)

All subjects will be strongly advised that they (or the female partners of male subjects) should not become pregnant while on study treatment or for the above-specified period after the last dose. A female subject will be advised that she must report immediately to the study site for pregnancy testing and appropriate management in the event that she may be pregnant.

(HMA, 2014)

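### New-pregnancy reporting ends at study exit (about Day 28) although contraception is required until 90 days after the last dose, and the SAE handling of a congenital anomaly is not stated

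*Protocol*

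**What the plan says.** Three parts of the protocol bear on when a pregnancy must be reported.

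- Section 12.4.5 sets the rule for new pregnancies after dosing starts: "any known cases of pregnancy in female subjects will be reported until the subject completes or withdraws from the study". Section 7.3 defines completion as finishing all study periods, "including the end of study visit on Day 28, which is the last" scheduled visit. The footnotes to Table 1 add that "All post-baseline visits are ± 1 day in the event a visit occurs on a weekend".
- Appendix 1 says that women of childbearing potential, and men whose partners are, "must use at least 1 highly effective method of contraception during the study and for 90 days after the last dose of study treatment". Inclusion criterion 7 in Section 8.1 sets the same period. Appendix 1 also advises against pregnancy during that period, and tells a woman who may be pregnant to contact the site at once.
- Section 12.4.5 has further sentences that reach past Day 28. One reads: "The investigator should also be notified of pregnancy occurring during the study but confirmed after completion of the study". Another, with no end date, says that when a subject is later discovered to be pregnant, the pregnancy is followed to term and the outcome goes to the sponsor after delivery. A partner's pregnancy is reportable within 24 hours of knowledge, again with no stated end date.

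On fetal outcomes, Section 12.4.2 includes among its SAE criteria an event that "is a congenital anomaly/birth defect". Section 12.4.3 limits the duty: "An SAE occurring from the first dose administered until Day 28 must be reported". Section 12.4.5 requires a congenital anomaly, abortion, stillbirth or neonatal death to be sent on the pregnancy form within 24 hours of knowledge, with no Day 28 limit. It also says that the pregnancy itself is not processed as an SAE.

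**The concern.** The sponsor asks subjects to avoid pregnancy for 90 days after the last dose, but asks sites to report new pregnancies only until the subject leaves the study. Most of the 90 days falls after that. The only scheduled pregnancy test is at screening, so later detection depends on passive reporting, and the reporting window is then the main control. Two sites that learn of a pregnancy conceived after Day 28 could handle it differently, and each could cite Section 12.4.5.

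The second issue is classification. If an anomaly is an SAE by definition but SAE reporting closes at Day 28, the reader cannot tell whether an anomaly that arrives months later on a pregnancy form should also go through SAE and SUSAR assessment.

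At stake is consistent capture of a rare safety event. Sample size, power, type 1 error and the efficacy analyses are not involved.

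**Working it through.** The documents give no figure of their own for this gap, so there is nothing to reproduce. The check is day arithmetic, followed by a comparison of the passages.

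**Inputs**
- Start of the day count: "Study Day 1= first dose of study drug" (footnote to Table 1).
- Treatment duration: 14 days (Section 9.2; Table 1 marks dosing on Days 1 to 14).
- Contraception period: 90 days after the last dose (Section 8.1 and Appendix 1).
- End of study: Day 28, ± 1 day (Section 7.3 and Table 1).
- Early Termination visit: 3 to 7 days after the last dose (Section 8.5).

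**Arithmetic**
- Last scheduled dose = 1 + 14 − 1 = Day 14.
- End of contraception period = 14 + 90 = Day 104.
- Days of that period covered by reporting to Day 28 = 28 − 14 = 14.
- Days not covered = 104 − 28 = 76, and 76/90 = 84%.
- If the last visit is on Day 27: 104 − 27 = 77 (86%). If it is on Day 29: 104 − 29 = 75 (83%).
- If contact ends at an Early Termination visit: 90 − 7 = 83 (92%) to 90 − 3 = 87 (97%).
- If a subject stops drug early on Day d but is followed to Day 28, the gap is (d + 90) − 28 = d + 62 days, which gives 76 at d = 14 and less for earlier stops.

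**Do the other sentences close the gap?** Take a conception on Day 40, reported to the site on Day 70.
- The rule in Section 12.4.5 ended at completion, so it does not apply.
- The sentence on late confirmation applies only to a pregnancy that occurred during the study. This one did not.
- The sentence on a subject later discovered to be pregnant could be read to apply, because it has no end date. That reading conflicts with the explicit stop in the same section.
- Appendix 1 brings the woman to the site, for testing and management. It does not tell the site to report to the sponsor.

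So the text is in conflict rather than silent, and no sentence clearly creates the duty.

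**Congenital anomaly.** After a negative urine test at screening, a subject's pregnancy could not plausibly reach delivery by Day 28. The SAE criterion in Section 12.4.2 therefore has almost no practical content inside the window in Section 12.4.3. The pregnancy form in Section 12.4.5 carries the anomaly to the sponsor at any date, but no passage says whether that report is then handled as an SAE. Section 12.4.4 starts SUSAR classification from adverse events that are serious, and does not mention the pregnancy form.

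**The case against.** Several stronger readings are tempting, and the documents do not support them.

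- *Adverse fetal outcomes would go unreported or lack a fast route.* They would not. Section 12.4.5 requires a report to the sponsor or its pharmacovigilance vendor within 24 hours of knowledge, with no Day 28 limit, and known pregnancies are followed to their end.
- *An anomaly can never become an SAE or a SUSAR.* The text does not say so. Section 12.4.2 lets either the sponsor or the investigator judge an event serious, and it must then be evaluated for expedited reporting. The SUSAR criteria in Section 12.4.4 carry no time limit. Section 12.4.3 limits the site's SAE reporting duty, not the sponsor's assessment of what it has received. Section 12.4.5 exempts the pregnancy from SAE processing and says nothing of the kind about an anomaly.
- *A site that learns of a pregnancy on Day 50 has no duty at all.* Such a pregnancy may have been conceived during the study, and then the late-confirmation sentence covers it. If it was conceived later, the undated sentence may reach it.
- *The 84% is a share of exposure or risk.* The documents call the 90 days a contraception period. Section 7.2 gives a half-life of about 75 minutes, so five half-lives take 5 × 75 = 375 minutes, or 6.25 hours. Conceptions during dosing fall inside the study and are covered. The 84% is a share of calendar days only, and the documents give no expected number of pregnancies.
- *Everyone who withdraws leaves 83 to 87 days uncovered.* Sections 8.5 and 12.4.1 intend follow-up to Day 28 after early termination. The range applies only where contact really ends at that visit, for example when consent is withdrawn.

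These objections stand and narrow the point. They do not remove the mismatch between the stated end of reporting and the 90-day period, or the missing statement on the SAE status of an anomaly.

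**Conclusion.** The point holds as an inconsistency in safety reporting. For a subject dosed through Day 14 and followed to Day 28, reporting of new pregnancies covers 14 of the 90 days for which the protocol requires contraception and leaves 76 uncovered, or 75 to 77 with the visit window. The gap is larger where follow-up ends before Day 28. Within it, a newly conceived pregnancy has no clear duty of reporting to the sponsor. Separately, an anomaly would reach the sponsor, but Sections 12.4.2, 12.4.3 and 12.4.5 do not together say how it is classified.

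This assumes a last dose on Day 14 and takes the explicit stop in Section 12.4.5 at its word over the undated sentence that follows. The affected events are likely to be few, though the documents give no figure for this. The correction is worth making because the mismatch is plain and the change is small.

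**What to change.** - In Section 12.4.5, replace the end point of completion or withdrawal with *through 90 days after the last dose of study drug*. Apply it to female subjects and to partners of male subjects, including those who withdraw. This uses the protocol's own contraception period and removes the conflict with the undated sentence.
- Add one line to the existing Day 28 call, and to the Early Termination visit, reminding subjects to contact the site if a pregnancy occurs in that period.
- Reconcile Sections 12.4.2, 12.4.3 and 12.4.5 by stating that a congenital anomaly reported on the pregnancy form is also assessed as an SAE regardless of the Day 28 limit. That single report should serve both purposes, so that sites do not file two.

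For a subject dosed through Day 14, pregnancy reporting would end on Day 104 instead of Day 28, which is 76 more days of passive reporting. The cost is amendment wording, one reminder line, and a few possible late reports to handle after the last Day 28 call. No visit, test or staff is added. The safety endpoints that run to Day 28 and all efficacy analyses stay as they are.
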